9.8. Early Discontinuation/Withdrawal of Participants

During the course of the study a participant may choose to withdraw early from the study treatment at any time. This may happen for several reasons, including but not limited to:

- Inability to comply with study procedures
- Participant decision

If a participant chooses to stop study assessments then all of their identifiable data will be destroyed, but all prior collected data assigned to the non-identifiable study ID will be retained. The participant will not be further contacted by the study team.

In addition, the Investigator may discontinue a participant from the study treatment at any time if the Investigator considers it necessary for any reason including, but not limited to:

- Ineligibility (either arising during the study or retrospectively having been overlooked at screening)
- Significant protocol deviation

9.9. Definition of End of Study

The end of study is the point at which all the study data has been entered and queries resolved.

10. SAFETY REPORTING

Considering that this is purely an observational study, there are no foreseeable potential serious adverse events.

11. STATISTICS AND ANALYSIS

11.1. Statistical Analysis Plan (SAP)

The plan for the statistical analysis of the study are outlined below. There is not a separate SAP document in use for the study.

11.2. Description of the Statistical Methods

For the primary outcome, the baseline and 12-month HRQoL assessments will be used for analysis. For all patients, comparison will be made between baseline and 12-months, but both will also be compared against the UK normative datasets.

For the secondary outcome pertaining to the sub-group undergoing decompressive surgery, HRQoL data will be similarly be compared to baseline and to UK normative datasets. Further comparisons of outcome data will be made between specific surgical techniques used, baseline symptoms and radiological findings.

Descriptive statistics will be used to report the data from the exploratory objective, regarding referral pathways, investigations and management strategies for CM1 in UK neurosurgical practice.

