3. SYNOPSIS

Study Title	UK Chiari 1 Study		
Internal ref. no. / short title	UK Chiari 1 Study		
Study registration	Oxford PID 269739.		
Sponsor	Oxford University Hospitals NHS Foundation Trust/University of Oxford Research and Development Department, Joint Research Office, Oxford University Hospitals NHS Foundation Trust, [name]; [contact] ; [name]		
Funder	The Ann Conroy Trust; www.annconroytrust.org Chair: [name]; Consultant Neurosurgeon; Department of Neurosurgery, Queen Elizabeth Hospital, Birmingham University Hospitals NHS Foundation Trust; [contact] ; [name]		
Study Design	Prospective, observational, multicentre, cohort study.		
Study Participants	Adults and children referred to neurosurgery clinic for Chiari 1 malformation (CM1)		
Sample Size	500 patients		
Planned Study Period	Total study duration (per site): 36-months Total study duration (for entire study): 42-months Recruitment period duration (per site): 12-months Follow up data for all patients: 12-months following recruitment Additional follow up for patients undergoing decompressive surgery: 12-months following date of decompressive surgery End date (for entire study): 6 th April 2024		
Planned Recruitment period	Participating sites may commence a 12-month recruitment period starting between 8 th October 2020 to 7 th April 2021.		
	Objectives	Outcome Measures	Timepoint(s)
Primary	To determine change in patient- or parent-reported, health-related quality of life (HRQoL) 12 months following first neurosurgical clinic	36-Item Short Form Health Survey (SF-36; UK version) in adults (16 years and above). Age-appropriate parent-reported Pediatric Quality of Life Inventory™ (PedsQL™; UK version) in children (2-15 years).	Baseline and 12-months following baseline
Secondary	To determine health-related quality of life 12-	HRQoL (as per baseline)	Baseline and 12-months following decompressive

	months following decompressive surgery [sub-set of patients undergoing decompressive surgery]		surgery
	To measure complications and need for re-operation 12-months following decompressive surgery [sub-set of patients undergoing decompressive surgery]	Rates of complications and need for further operations following decompressive surgery	12-months following decompressive surgery

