7. STUDY DESIGN

The *UK Chiari 1 Study* will be a prospective, multi-centre cohort study and will be complete after three years. The study is purely observational and will not alter patient care in any way.

The study will collect both patient- or parent- reported (hereafter referred to as patient-reported) and surgeon-reported data. The study design allows for remote, online data collection and therefore does not require further visits to the hospital or any other facility. Participants will be required to provide patient-reported data at baseline and 12-months following baseline. Additionally, if the patient undergoes a decompressive surgery, then they will be asked to provide patient-reported data 12-months after their surgery. The maximum duration of follow up following baseline, therefore, will be 12-months for patients who do not undergo decompressive surgery and 24-months for patients who do undergo decompressive surgery.

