9.6. Baseline Assessments

Patient-reported data at baseline will consist of an online questionnaire, including the baseline HRQoL assessment. For a patient's baseline HRQoL to be included in the analysis, the questionnaire must have been completed by 45-days after being seen in the neurosurgical clinic.

Surgeon-reported data at baseline will be by review of clinical records by the study team at the participating NSU.

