9.7. Subsequent Assessments

All patients will be followed up at 12-months following first neurosurgical clinic attendance. Patients will be sent an email with a link to the online questionnaire. Either the local study team or steering committee may phone the patient if there is no response to the online questionnaire after seven days.

Surgeon-reported data based on clinical records will also be inputted to the database at the 12-month mark. At the time of this data review, the local investigators will identify a sub-group of the patients who have undergone decompressive surgery since enrolment in the study. For patients who have undergone decompressive surgery, an additional 12-month follow up questionnaire shall be scheduled. Similarly, this sub-group of patients will be sent an email with a link to their questionnaire 12-months after their

operation and the study team or steering group may follow up with a phone call, if necessary, after seven days.

For each follow up timepoint, patient-reported data (i.e. questionnaires) must be completed within 45-days from the target date to be included in the analysis).

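### The post-surgical HRQoL change is measured from the first-clinic baseline, up to 12 months before the operation, so it and any technique comparison based on it can be confounded by waiting time

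*Protocol*

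**What the plan says.** The synopsis sets the timepoints for HRQoL in the decompression sub-set as "Baseline and 12-months following decompressive" surgery. Section 11.2 gives the analysis: "For the secondary outcome pertaining to the sub-group undergoing decompressive surgery, HRQoL data will be similarly be compared to baseline and to UK normative datasets". It then adds comparisons of outcome between surgical techniques. It does not mention the time from baseline to operation.

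Baseline is anchored to the clinic visit, not to surgery. Under section 9.6, for the baseline HRQoL to count, "the questionnaire must have been completed by 45-days after being seen in the neurosurgical clinic".

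Section 7 lists the patient-reported collections. "Participants will be required to provide patient-reported data at baseline and 12-months following baseline". In addition, "if the patient undergoes a decompressive surgery, then they will be asked to provide patient-reported data 12-months after their surgery". The maximum follow-up after baseline is "12-months for patients who do not undergo decompressive surgery and 24-months for patients who do undergo decompressive surgery".

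Section 9.7 says how the surgical group is found, at the 12-month record review: "At the time of this data review, the local investigators will identify a sub-group of the patients who have undergone decompressive surgery since enrolment in" [...].

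Section 11.1 says that no separate analysis plan is in use, so section 11.2 is where this comparison is defined.

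**The concern.** For an operated patient, the difference between the post-operative score and baseline has two parts: what happened between the baseline questionnaire and the operation, and what happened in the 12 months after it. Only the second part follows decompression. With no score near the operation, the two cannot be separated.

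Stability during the wait cannot be taken for granted. Section 5 describes the natural history as poorly understood, and section 6 makes the course of conservatively treated patients an objective of its own. A patient who loses 10 points while waiting and regains 10 after surgery is recorded as unchanged. A patient who was already improving carries that gain into the post-surgical result.

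The technique comparisons are the most exposed. Section 5 says that technique varies between centres and surgeons. If waits also vary between centres, a comparison of techniques on change from baseline is partly a comparison of waiting times. The lay summary and section 5 show that the study hopes to inform the choice of patients and technique, so the result is likely to be read in that way.

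**Working it through.** **Inputs**
- Maximum follow-up from baseline, operated patients: 24 months (section 7).
- Post-operative questionnaire: 12 months after surgery (sections 7 and 9.7).
- Surgical group: patients decompressed between enrolment and the 12-month record review (section 9.7).
- Baseline questionnaire: up to 45 days after first clinic (section 9.6).
- Distribution of waits and HRQoL drift while waiting: not given.

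**Step 1: reproduce the protocol's figure.** Latest operation that the 12-month review can pick up (12 months) + post-operative follow-up (12 months) = 24 months. This matches "24-months for patients who do undergo decompressive surgery". Conversely, the longest wait is 24 − 12 = 12 months.

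**Step 2: span of the change score.** With wait *w* in months, the span is *w* + 12 and the share before decompression is *w* / (*w* + 12).

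| Wait *w* | Span | Share before decompression |
|---|---|---|
| 0 | 12 | 0/12 = 0% |
| 3 | 15 | 3/15 = 20% |
| 6 | 18 | 6/18 = 33% |
| 9 | 21 | 9/21 = 43% |
| 12 | 24 | 12/24 = 50% |

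These are nominal times, ignoring the 45-day questionnaire windows. Section 9.6 has no rule that the baseline form must precede surgery. After a very early operation it could therefore be completed up to about 45 days after the procedure, so the interval from questionnaire to operation can even be negative.

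**Step 3: does another scheduled form fill the gap?** The questionnaire at 12 months after baseline does not. For patients operated on within the year it normally falls after surgery, at a post-operative time that varies with the wait. Sections 6, 7, 9.5.1 and 9.7 and Appendix B list no other HRQoL assessment.

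**Step 4: size, as illustration only.** If HRQoL drifts by *d* points a month before surgery, the wait adds *d* × *w* to the change score. Take *d* from −0.5 to +0.5 (an assumption with no basis in the protocol). The contribution is 0 at no wait, ±1.5 at 3 months, ±3.0 at 6, ±4.5 at 9 and ±6.0 at 12.

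The mean contribution depends on the waits, which must also be assumed:
- Uniform over 0 to 12 months: mean wait 6.0 months and 75% over 3 months, so ±0.5 × 6.0 = ±3.0 points.
- Front-loaded (exponential with median 4 months before truncation at 12, about 3.3 months after it): mean wait 4.06 months and 54% over 3 months, so ±0.5 × 4.06 = ±2.0 points.

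Both means assume that all patients drift in the same direction. With mixed directions the mean shift shrinks towards zero, while individual change scores remain distorted.

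**The case against.** The protocol nowhere calls this difference an effect of surgery. Secondary objective 1 is the HRQoL level 12 months after decompression, and half of the planned comparison, that with UK norms, does not depend on the baseline. A reader might infer that the plan claims a surgical effect and estimates it with bias. The text does not support that inference, and this part of the objection stands.

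First clinic is also a sensible common origin. Operated and unoperated patients share it, and it serves the primary outcome. It is a design choice, not an error. That also stands, but it justifies the baseline, not silence about the interval.

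Nor would a pre-operative score settle the matter. In an uncontrolled before/after comparison, patients measured at their worst just before surgery would tend to improve by regression to the mean. A form re-sent only after a long wait would create two definitions of the reference score, split by waiting time itself, and would add site work, because surgical cases are now identified at one review. These arguments stand against requiring such a form.

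Finally, a reader might suppose that late operations mark patients who worsened after clinic. Nothing in the protocol says so, and long waits may equally reflect queues.

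What the objection does not remove is that section 11.2 compares with baseline and compares techniques, with no account taken of an interval that varies by up to 12 months.

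**Conclusion.** The point holds as a limitation of how a secondary outcome is analysed and labelled. It rests on the protocol's own timeline: a wait of 0 to 12 months, a span of 12 to 24 months, and 0% to 50% of the span before decompression. Twelve months is an upper bound, and how many patients come near it is unknown.

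No numerical bias can be stated. The drift and waiting-time figures in the working are assumptions that show scale only. It would go too far to say that the surgical result is biased by a given number of points, or in a given direction. What can be said is that the change from baseline, and any technique comparison built on it, can be confounded by waiting time. The norm comparison and the primary outcome are outside this point.

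**What to change.** Amend section 11.2 as follows:

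1. Label the comparison with baseline as *change since first neurosurgical clinic*, so that it is not read as change attributable to surgery.
2. Report the distribution of the interval from baseline questionnaire to operation, overall and by technique.
3. Include that interval as a covariate in the change analysis and in technique comparisons based on change, separately for adults and children as section 11.4 already requires.
4. Add a sensitivity analysis restricted to patients with a short interval, for example 3 months or less. The cut-off is arbitrary and should be stated in advance.

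The cost is a few sentences and a little more analysis. The full data-field list is not in the text at hand, but questionnaire and operation dates are needed to apply the 45-day windows and to schedule the post-operative form.

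The limits should be stated alongside. The short-interval set may differ in urgency and case mix, and the covariate cannot recover the unmeasured pre-operative score, so both analyses are supportive only. A repeat questionnaire before surgery is not needed for this fix and should be dropped or left optional, for the reasons given under the objection.

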11.3. Sample Size Determination

A pilot retrospective data review from two neurosurgical units (Birmingham and Oxford) showed that, in one month, one unit saw eleven and the other saw four patients that met the inclusion criteria aforementioned. Assuming a 50% recruitment rate, we would recruit around 90 patients in one year in these two units. Although we hope that more than 30 NSUs take part, if 12 similar sized units took part, we could potentially recruit >500 patients. These pessimistic estimates will account for some NSUs not taking part and also for patient withdrawals.

11.4. Analysis populations

Adult and paediatric HRQoL will be analysed separately since the measurement tools are different. Health related quality of life (HRQoL) will be measured in adults (16 years and above) using the 36-Item Short Form Health Survey (SF-36; UK version). HRQoL will be measured in children (2 – 15 years) using the Age-appropriate parent-reported Pediatric Quality of Life Inventory™ (PedsQL™; UK version). Children less than two years of age will be recruited into the study, but not included in the HRQoL analyses.

11.5. Decision points

Following the last possible date of patient recruitment (6th April 2022), a review of the number of recruited patients will be performed.

11.6. The Level of Statistical Significance

Statistical significance will be set at $p < 0.05$.

11.7. Procedure for Accounting for Missing, Unused, and Spurious Data.

For surgeon-reported data, the database entry system with standardised fields will prevent spurious or duplicate data input. If missing data is noted by the principal investigators, the local study team will be contacted and asked to provide the data.

For patient-reported data, if any duplicate questionnaires are filed, the first submitted questionnaire will be used. Patients may be contacted up to 45-days after the relevant past due assessment by the study team if there is a missing questionnaire.

11.8. Procedures for Reporting any Deviation(s) from the Original Statistical Plan

Deviations from the original statistical plan will be described and justified in protocol and/or in the final report, as appropriate).

12. DATA MANAGEMENT

The plan for the data management of the study are outlined below. There is not a separate Data Management document in use for the study.

12.1. Source Data

As described in 9.6.1, source data falls under two categories:

1. Patient-reported data (questionnaires)
2. Surgeon-reported data (medical records, theatre records and radiology)

All source data and documents will be stored securely on the REDCap database. On all study-specific documents, other than the signed consent, the participant will be referred to by the study participant number/code, not by identifiable information.

12.2. Access to Data

Direct access will be granted to authorised representatives from the Sponsor and host institution for monitoring and/or audit of the study to ensure compliance with regulations.

12.3. Data Recording and Record Keeping

Data will be entered onto a secure, online database platform called REDCap (<https://projectredcap.org/>) [13]. REDCap has been used extensively in clinical studies by the NHS and UK universities, including the recent DISCOVER study by the STARSurg collaborative [14]. Online data capture has been used successfully by previous BNTRC studies, such as the Understanding Cauda Equina Study [15].

All information will be kept strictly confidential and the study will comply with the Data Protection Act 1998 and the EU General Data Protection Regulation (GDPR).

Every member of the local study teams will be given personal log-in details in order to input and access data to and from the database. Local study team members will have full access to their local data, but not the data of other participating NSUs. The lead/Sponsor site (Oxford) will have full access to all of the data (from every NSU) to allow multicentre data analysis, ensure ongoing validity of the study or to follow up with patients. The REDCap system also allows the lead/Sponsor site full visibility of the electronic audit trail that tracks all user activity on the database, allowing full accountability of its usage and to ensure standard operating procedures are maintained.

Once a patient electronically signs the consent form, the REDCap system will automatically assign the patient a unique UK Chiari 1 Study ID number. Each NSU will keep a log of the corresponding local ID number or NHS number on their local secure NHS system. With their consent, each patient's email address and phone number will be securely stored on the database and is hidden behind access controls

so that only the local collaborator and principal investigators can see them. Other than on the consent form, the name and any other identifying detail will not be included in any study data electronic file.

Following completion of the study, all data recorded on the database will be downloaded by the sponsor site and retained within the secure electronic NHS system for at a maximum of 10 years following completion of the study. Data, including the separately stored consent forms, will be retained further if patients have been consented to being contacted for future studies.

13. QUALITY ASSURANCE PROCEDURES

Quality assurance procedures will be conducted by the Sponsor site. The study may be monitored, or audited in accordance with the current approved protocol, GCP, relevant regulations and standard operating procedures.

13.1. Study Committees

The *UK Chiari 1 Study* will be overseen by the *UK Chiari 1 Study* steering committee, who will meet at least six-monthly to ensure ongoing validity of the study.

The *UK Chiari 1 Study* was selected for support by the BNTRC following an open, national call for projects in 2018. It has been reviewed by the BNTRC committee, the Society of British Neurological Surgeons (SBNS) Academic Committee, and the British Syringomyelia Chiari Group (BSCG).

14. PROTOCOL DEVIATIONS

A study related deviation is a departure from the ethically approved study protocol, other study document or process or from Good Clinical Practice (GCP) requirements. Any deviations from the protocol will be documented in a protocol deviation form and filed in the study master file.

A standard operating procedure should be in place describing the procedure for identifying non-compliances, escalation to the central team and assessment of whether a non-compliance /deviation may be a potential Serious Breach.

15. SERIOUS BREACHES

A “serious breach” is a breach of the protocol or of the conditions or principles of Good Clinical Practice which is likely to affect to a significant degree –

- (a) the safety or physical or mental integrity of the study subjects; or
- (b) the scientific value of the research.

In the event that a serious breach is suspected the Sponsor must be contacted within 1 working day. In collaboration with the C.I., the serious breach will be reviewed by the Sponsor and, if appropriate, the Sponsor will report it to the approving REC committee and the relevant NHS host organisation within seven calendar days.

16. ETHICAL AND REGULATORY CONSIDERATIONS

16.1. Declaration of Helsinki

The Investigator will ensure that this study is conducted in accordance with the principles of the Declaration of Helsinki.

16.2. Guidelines for Good Clinical Practice

The Investigator will ensure that this study is conducted in accordance with relevant regulations and with Good Clinical Practice. Whilst it is not an absolute requirement, we would encourage all collaborators to complete their Good Clinical Practice (GCP) training prior to the start of their involvement in the study.

16.3. Approvals

Following Sponsor approval, the protocol, informed consent form and participant information sheet will be submitted to an appropriate Research Ethics Committee (REC), and HRA (where required) and host institutions for written approval.

The Investigator will submit and, where necessary, obtain approval from the above parties for all substantial amendments to the original approved documents.

